8.2 Investigational drug Assignment and Dispensing Procedures

Subjects will be assigned to receive their treatment according to the schedule allocated to each study site.

After ICF signing the investigator or investigator's designee will access the IVRS/IWRS to obtain the subject study number.

The investigator or the investigator's designee will utilize the IVRS/IWRS to randomize the subject into the study. The medication identification (ID) number of the investigational drug will then be provided by the IVRS/IWRS. The investigational drug will be dispensed on the Baseline visit.

8.3 Randomization Code Creation and Storage

The randomization code will be assigned via IVRS/IWRS.

8.4 Investigational Drug Blind Maintenance

The investigational drug blind will be maintained using the IVRS/IWRS.

8.5 Unblinding Procedure

The investigational drug blind shall not be broken by the investigator unless information concerning the investigational drug is necessary for the medical treatment of the subject. In the event of a medical emergency, if possible, the medical monitor should be contacted before the investigational drug blind is broken to discuss the need for unblinding.

For unblinding a subject, the investigational drug blind can be obtained by the investigator, by accessing the IVRS/IWRS.

The sponsor must be notified as soon as possible if the investigational drug blind is broken. The date, time, and reason the blind is broken must be recorded in the source documents and the same information (except the time) must be recorded on the (e)CRF.

If any site personnel are unblinded, investigational drug must be stopped immediately and the subject must be withdrawn from the study.

8.6 Accountability and Destruction of Sponsor-Supplied Drugs

Drug supplies will be counted and reconciled at the site before being returned to the sponsor or designee.

The investigator or designee must ensure that the sponsor-supplied drug is used in accordance with the protocol and is dispensed only to subjects enrolled in the study. To document appropriate use of sponsor-supplied drug (Cyclobenzaprin or placebo), the investigator or designee must maintain records of all sponsor-supplied drug delivery to the site, site inventory, dispensation and use by each subject, and return to the sponsor or designee.

Upon receipt of sponsor-supplied drug, the investigator or designee must verify the contents of the shipments against the packing list. The verifier should ensure that the quantity is correct, and the medication is in good condition. If quantity and conditions are acceptable, investigator or designee should acknowledge the receipt of the shipment by signing bottom half of the packing list and sending by e-mail per instructions provided at site initiation visit. If there are any discrepancies between the

packing list versus the actual product received, Takeda and/or its designee must be contacted to resolve the issue. The packing list should be filed in the investigator's essential document file.

The investigator or designee must maintain 100% accountability for all sponsor-supplied drugs, received and dispensed during his or her entire participation in the study. Proper drug accountability includes, but is not limited to:

- Continuously monitoring expiration dates
- Frequently verifying that actual inventory matches documented inventory.
- Verifying that the log is completed for each Medication ID number received / dispensed at the site.
- Verifying that all containers used are documented accurately on the log.
- Verifying that required fields are completed accurately and legibly.

If any dispensing errors or discrepancies are discovered, the sponsor must be notified immediately.

The IVRS/IWRS will include all required information as a separate entry for each subject to whom sponsor-supplied drug is dispensed.

The investigator or designee must record the current inventory of all sponsor-supplied drugs on a sponsor-approved drug accountability log. The following information will be recorded at a minimum: protocol number and title, name of investigator, site identifier and number, description of sponsor-supplied drugs, expiry date and amount dispensed including initials, seal, or signature of the person dispensing the drug, and the date and amount returned to the site by the subject, including the initials, seal, or signature of the person receiving the sponsor-supplied drug. The log should include all required information as a separate entry for each subject to whom sponsor-supplied drug is dispensed.

All study drug that was not returned to the site by a subject must be investigated by the site and appropriately documented on the drug accountability log.

Prior to site closure or at appropriate intervals, a representative from the sponsor or its designee will perform sponsor-supplied drug accountability and reconciliation before sponsor-supplied drugs are returned to the sponsor or its designee for destruction. The investigator or designee will retain a copy of the documentation regarding sponsor-supplied drug accountability, return, and/or destruction, and originals will be sent to the sponsor or designee.

The investigator will be notified of any expiry date or retest date extension of sponsor-supplied drug during the study conduct. On expiry date notification from the sponsor or designee, the site must complete all instructions outlined in the notification, including segregation of expired sponsor-supplied drug for return to the sponsor or its designee for destruction.

In the event of expiry date extension of sponsor-supplied drug already at the study site, sponsor-supplied drugs may be relabeled with the new expiry date at that site. In such cases, Takeda or its designee will prepare additional labels, certificates of analyses, and all necessary documentation for completion of the procedure at the sites.

9.0 STUDY PLAN

9.1 Study Procedures

The following sections describe the study procedures and data to be collected. For each procedure, subjects are to be assessed by the same investigator or site personnel whenever possible. The Schedule of Study Procedures is located in [Appendix A](#).

9.1.1 Informed Consent Procedure

The requirements of the informed consent are described in Section 15.2.

Informed consent must be obtained prior to the subject entering into the study, and before any protocol-directed procedures are performed.

A unique subject identification number (subject number) will be assigned to each subject at the time that informed consent is obtained; this subject number will be used throughout the study.

9.1.2 Demographics, Medical History, and Medication History Procedure

Demographic information to be obtained will include date of birth, sex, race as described by the subject, and smoking status of the subject at Screening.

Medical history to be obtained will include determining whether the subject has any significant conditions or diseases relevant to the disease under study that stopped at or prior to signing of informed consent. Ongoing conditions are considered concurrent medical conditions (see Section 9.1.8).

Medication history information to be obtained includes any medication relevant to eligibility criteria and efficacy/safety evaluation stopped at or within 14 days prior to signing of informed consent.

9.1.3 Physical Examination Procedure

A baseline physical examination (defined as the assessment prior to first dose of investigational drug) will consist of the following body systems: (1) eyes; (2) ears, nose, throat; (3) cardiovascular system; (4) respiratory system; (5) gastrointestinal system; (6) dermatologic system; (7) extremities; (8) musculoskeletal system; (9) nervous system; (10) lymph nodes; and (11) other (if applicable). All subsequent physical examinations should assess clinically significant changes from the assessment prior to first dose examination.

9.1.4 Weight, Height

A subject should have weight and height measured while wearing indoor clothing and with shoes off.

9.1.5 Vital Sign Procedure

Vital signs will include sitting blood pressure (resting more than 5 minutes), and pulse (bpm).

9.1.6 Primary Efficacy Measurement

The measures of effectiveness in this study will include:

- **Subject's rating of medication helpfulness:**

Subjects will be asked to assess it on a daily basis (in the daily diary), using the following 5-point rating scale: "How would you rate this study medication in improving your condition?"

"0 = poor"

"1 = fair"

"2 = good"

"3 = very good"

"4 = excellent"

Assessment of the subject's answers will be made for the Day 3, 7 and 15.

- **Physician's clinical global assessment :**

The investigator will be asked to assess their clinical global impression of change compared to Baseline, based on physical examination, degree of muscle spasm (presence of muscle spasm assessment), reaction to palpation (presence of local pain assessment), limitation of range of motion, and evaluation of the patient's reported functional assessment (limitation of activities of daily living assessment). The following 5-point rating scale will be used:

"1 = worse"

"2 = no change"

"3 = slight improvement"

"4 = moderate improvement"

"5 = marked improvement"

Assessment will be made for the Day 3, 7 and 15.

- **The subject-rated relief from local pain:**

Subjects will be asked to assess on a daily basis (in the daily diary) their level of relief from local pain due to the muscle spasm (in either the lower back or cervical spine) compared to Baseline (Visit 1) using the following 5-point rating scale:

"1 = no relief"

"2 = a little relief"

"3 = some relief"

"4 = a lot of relief"

"5 = complete relief"

Assessment of the subject's answers will be made for the Day 3, 7 and 15.

- **The subject-rated restriction in activities of daily living:**

Subjects will be asked to assess on a daily basis (in the daily diary) the change in the severity of restriction in the activities of daily living compared to Baseline (Visit 1) using the following 5-point rating scale:

"1 = worsening"

"2 = no change"

"3 = mild improvement:"

"4 = moderate improvement"

"5 = marked improvement"

Assessment of the subject's answers will be made for the Day 3, 7 and 15.

CONFIDENTIAL

- **The subject-rated restriction of movement:**

Subjects will be asked to assess on a daily basis (in the daily diary), the change in restriction of movement due to the muscle spasm compared to Baseline (Visit 1) using the following 5-point rating scale:

“1 = no relief”

“2 = a little relief”

“3 = some relief”

“4 = a lot of relief”

[figure not shown]
“5 = complete relief”

Assessment of the subject’s answers will be made for the Day 3, 7 and 15.

- **The subject-rated intensity of local pain:**

Subjects will be asked to assess on a daily basis (in the daily diary) their intensity of local pain due to the muscle spasm (in either the lower back or cervical spine) using the following digital rating scale. It is necessary to mark the intensity of pain by circling a one of the 11 points from 0 "No Pain" to 10 "Severe Pain" with an intermediate value of 5 - "Moderate Pain".

Facial pain scale is presented to help the patient to identify the primary area of the intensity of the pain experienced:

Assessment of the subject’s answers will be made for the Day 3, 7 and 15.

- **Subject-Rated Clinical Global Impression:**

[figure not shown]
Subjects will be asked to assess on a daily basis (in the daily diary) their clinical global impression of change compared to Baseline, based on rating on medication helpfulness, relief from local pain, restriction in activities of daily living, restriction of movement.

Assessment of the subject’s answers will be made for the Day 3, 7 and 15.

Company Confidential Information

Company Confidential Information

Company Confidential Information

- Hematology, blood chemistry, urinalysis, urine pregnancy testing (if applicable), vital signs, physical examinations, and ECGs will be performed at Screening and study termination. Vital signs will be recorded at each clinic visit. Monitoring and recording of AEs will be performed during each clinic visit and continued for 3 weeks after the last dose of study drug.

Other assessments:

- **Presence of muscle spasm**

The physician was asked to evaluate the presence of muscle spasm by palpation (increased consistency of a muscle or group of muscles) using the following 5-point rating scale at each visit:

“1 = none” (no muscle spasm present)

“2 = mild” (the muscle is somewhat harder than usual)

“3 = moderate” (muscles are hard and borders of increased consistency can be determined by palpation)

“4 = moderately severe” (muscles are very hard and borders are sharply defined by palpation)

“5 = severe” (board-like hardness of the muscles)

- **Presence of local pain**

The physician was asked to assess the presence of local pain due to muscle spasm by palpation (tenderness on palpation) using the following 5-point rating scale at each visit:

“1 = none” (no pain)

“2 = mild” (complaint of local discomfort on palpation)

“3 = moderate” (objective evidence that the area is painful, such as defensive movements, reflex dilatation of pupils, etc.)

“4 = moderately severe” (the area is very painful)

“5 = severe” (the area is intolerably painful and subject objects to the examination)

CONFIDENTIAL

- **Limitation of range of motion**

The physician was asked to assess at each visit, the subject's limitation of range of motion using the following 5-point rating scale:

"1 = none" (no limitation in range of motion)

"2 = mild" (restriction of the normal motion by 10-15%)

"3 = moderate" (restriction of the motion by no more than 50%)

"4 = moderately severe" (restriction of the expected motion by no more than 80%)

"5 = severe" (the subject has great difficulty in attempting to perform one or more of the major motions)

- **Limitation of activities of daily living**

The physician was asked to assess by both direct observation and historical questioning, the limitation of activities of daily living using the following 5-point rating scale at each visit:

"1 = none" (no limitation of activities of daily living)

"2 = mild" (the subject is able to perform his customary tasks, but with discomfort)

"3 = moderate" (the subject is able to perform partially with discomfort some essential tasks and activities)

"4 = moderately severe" (the subject performs partially with great difficulty some essential tasks and activities)

"5 = severe" (the subject is unable to perform most of the essential tasks or activities)

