5.2.2 Secondary Endpoints

- The percentage of subjects with physician's clinical global assessment on Day 3 of treatment.
- The percentage of subjects with subject's rating of medication helpfulness impression on Day 7 and 14 of treatment.
- The percentage of subjects with physician's clinical global assessment on Day 7 and 15 of treatment.
- The percentage of subjects with subject-rated global impression (relief from local pain, restriction in activities of daily living, restriction of movement, intensity of local pain) of on Day 3, 7 and 14 of treatment.
- The percentage of subjects defined as responders on Day 3, 7 and 14 of treatment.
- The percentage of subjects with physician rated assessment of presence of muscle spasm, presence of local pain, limitation of range of motion, limitation of activities of daily living on Day 3, 7 and 15.

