9.3.2 Randomization

Randomization will take place on Day1 (could be the same day at which Screening visit took place). The following procedures will be performed and documented during Randomization:

- Vital Signs (if not same day as Screening procedures).
- Concomitant medications.
- Adverse Events.
- The following parameters will be assessed by the investigator: presence of muscle spasm, presence of local pain, limitation of activities of daily living, and limitation of range of motion.
- Subject Diary dispense. Subjects should be instructed :
 - To complete assessment for Day 1 at the hospital before the first drug intake.
 - Starting from Day 2 record the following assessments (compared to Baseline) in the daily diary: rating of medication helpfulness, relief from local pain, subject-rated Clinical global impression, restriction in activities of daily living, and restriction of movement;
 - To record the following assessments in the daily diary: **Company Confidential Information** intensity of local pain **Company Confidential Information** ;
 - To complete their diary during 14 days at the same time each day if possible but record the worst feeling/symptom since the diary was last completed. No diary to be completed at Day 15 (Visit 4) but returned to the Investigator.
 - To bring their diary to each study visit for review by Investigator. Completed pages will be collected by Investigator, then the diary will be dispensed to subject again.
- If the subject has satisfied all of the inclusion criteria and none of the exclusion criteria for randomization, the subject should be randomized using the IVRS/IWRS, as described in Section 8.2.
- Study drug dispense. The medication identification (ID) number of the study drug will be provided via IVRS/IWRS. To avoid any overdose and non-compliance with study drug intake, original bottle containing 60 capsules with CER 15 mg or Placebo will be opened in front of the subject and 40 capsules of 60 will be removed in cleanliness condition and put into the additional bottle for keeping at the site (never dispensed to subject) until destruction. Original bottle containing 20 capsules with CER 15 mg or Placebo will be dispensed to subject. Subject will be instructed to:
 - To swallow one capsule whole with 180 mL of room temperature water, once daily in the evening between 18:00 and 19:00 starting from Day1.

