Trends in the distribution of ratings by treatment group will be compared across the 3 visits to determine if there were any qualitative differences in the pattern of treatment response. Differences between treatments in the distribution of ratings at the 3 visits will be analysed using a weighted least squares model for marginal homogeneity including a parameter for treatment and treatment-by-visit interaction. Trends over time in the proportion of responders among the treatment groups will be assessed qualitatively by comparing the patterns of change in proportion of responders from Day 3 through Day 14. Repeated-measures analysis of proportions using Generalized Estimating Equations (GEE) will be used for comparisons among treatments of the trend in proportion of responders over time.

Time to improvement in subject's rating of medication helpfulness will be defined as the number of days from the start of treatment to the first time there was an assessment of "fair" to "excellent". If the subject did not have any improvement in their rating of medication helpfulness, time to improvement was censored and equaled the number of days from the start of treatment to the last measurement during the study. The Kaplan-Meier curves will be compared using the generalized Wilcoxon test for survival analysis.

Secondary Efficacy Endpoints

The following subject's ratings will be analyzed and summarized: relief from local pain due to muscle spasm, restriction in activities of daily living, restriction of movement, and clinical global impression. Time to improvement of subject-rated relief from local pain will be analyzed.

Subject Ratings

The subject's ratings will be analyzed separately for the differences between the Placebo and CER treatment group using a 2-sample Wilcoxon rank sum test.

Time to improvement of subject-rated relief from local pain will be defined as the number of days from the start of treatment to the first time there was an assessment of "a little relief" to "complete relief". If the subject did not have any improvement in their rating of relief from local pain, time to improvement was censored and equaled the number of days from the start of treatment to the last measurement recorded for the subject during the study. The Kaplan-Meier curves will be compared using the generalized Wilcoxon test for survival analysis.

Other Efficacy Endpoints

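### The subject-rated restriction-of-movement item asks for change from Baseline but offers only relief answers, so worsened and unchanged subjects get the same score

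*Protocol*

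**What the plan says.** Protocol 9.1.6 has subjects rate each day "the change in restriction of movement due to the muscle spasm compared to Baseline (Visit 1) using the following 5-point rating scale". The five answers are *no relief*, *a little relief*, *some relief*, *a lot of relief* and "5 = complete relief".

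The item just before it asks a parallel question, "the change in the severity of restriction in the activities of daily living compared to Baseline (Visit 1) using the following 5-point rating scale". Its answers start at 1 = *worsening* and 2 = *no change* and end at 5 = *marked improvement*. The physician's clinical global assessment in the same section likewise separates *worse* from *no change*. The relief answers are those of the local-pain item, which asks subjects for "their level of relief from local pain due to the muscle spasm".

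Section 5.2.2 includes the item among the components of a secondary endpoint ("restriction in activities of daily living, restriction of movement, intensity of local pain"). Section 13.1.3 says that the subject ratings "will be analyzed separately for the differences between the Placebo and CER treatment group using a 2-sample Wilcoxon rank sum test". Section 9.3.2 places it in the list introduced by "Starting from Day 2 record the following assessments (compared to Baseline) in the daily diary".

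**The concern.** A question about change can be answered in either direction, but this one can only be answered in one. A worsened subject has no truthful answer and falls back on *no relief*. An unchanged subject marks the same box, so the data cannot tell them apart.

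Some early worsening is plausible. Sections 7.2 and 7.3 bar NSAIDs, paracetamol and topical anti-inflammatory agents before entry and, except as rescue, during the study. Section 9.3.2 tells subjects to record the worst symptom since the last diary entry. If worsening differed between arms, whether it favoured CER or went against it, this item would not show it. The subject-rated global impression also draws on restriction of movement (9.1.6).

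**Working it through.** The protocol states no figure on this point, so the check compares question with answers and then follows the consequence into the rank test.

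**Questions and answers in 9.1.6**

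| Item | Question asks for | Score 1 | Score 2 | Score 5 | Levels for worsening |
|---|---|---|---|---|---|
| Restriction of movement (subject) | change | no relief | a little relief | complete relief | 0 of 5 |
| Activities of daily living (subject) | change | worsening | no change | marked improvement | 1 of 5 |
| Global assessment (physician) | change | worse | no change | marked improvement | 1 of 5 |
| Relief from local pain (subject) | relief | no relief | a little relief | complete relief | 0 of 5 |

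In the last row question and answers agree. In the first they do not. All five movement answers are legible, so this is not a gap in the extracted text. No other section gives a different scale or a rule for scoring worsening.

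**Can worsening be derived another way from this item?** No. Section 9.3.2 lists it from Day 2 only, relative to Baseline, and lists no pre-treatment self-rating of movement to compare against.

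**Consequence for the rank test.** Let θ be the probability that a CER subject scores better than a placebo subject, plus half the probability of a tie. Let w_P and w_C be the shares who worsen, and B_P and B_C the shares who are worse or unchanged.

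- Merged, the bottom group contributes B_P·B_C/2 to θ.
- Separated, it contributes w_P·w_C/2 + (B_C − w_C)·(B_P + w_P)/2.
- The difference is (B_C·w_P − B_P·w_C)/2. This is the information that the relief scale cannot carry.

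The protocol gives no shares, so these are assumed: 30% worse or unchanged in each arm, and four benefit grades of 30/20/15/5% on placebo and 22/22/19/7% on CER.

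- Merged: θ = 0.30×0.15 + 0.22×0.45 + 0.22×0.70 + 0.19×0.875 + 0.07×0.975 = 0.5325.
- Worsening 15% placebo, 5% CER: add 0.30×(0.15 − 0.05)/2 = 0.015, so θ = 0.5475.
- Worsening 5% placebo, 15% CER: subtract 0.015, so θ = 0.5175.
- Worsening 5% in both arms: no difference, θ = 0.5325.

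The relief scale returns 0.5325 in all three cases. The benefit grades are held fixed to isolate the missing level, so this is not a comparison of the two five-point scales.

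**The case against.** **Loss of power.** A reader might infer that the relief scale weakens the comparison. Assume 90 per arm and, over worse/no change/mild/moderate/marked, placebo 15/30/25/20/10% against CER 5/27/27/25/16%. Wilcoxon power is then about 60% with five levels and 48–49% with the lowest two merged. The documents do not support this as the size of the problem, for two reasons.

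- It compares five levels with four. The actual relief scale also has five: it lacks a level at the bottom but has four grades of benefit, against three on the daily-living scale. Dividing benefit into four can recover a few points, to roughly 50–54%.
- It assumes that worsening is three times as common on placebo. Keep the worse-or-unchanged shares at 45% and 32% but let 10% worsen in each arm. The difference in θ is then (0.32×0.10 − 0.45×0.10)/2 = −0.0065, and the daily-living scale has less power, about 41–42% against 48%. If worsening is rare, the two hardly differ.

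**Deterioration hidden from the trial.** This also goes too far. The daily-living item, the physician's global assessment, the daily 0–10 pain intensity and the physician-rated limitation of range of motion can all show it. None of them is the subject's own rating of movement, and 13.1.3 plans only frequency summaries for the range-of-motion rating.

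**Comparability between items.** A score of 2 means *no change* on one item and *a little relief* on the other. This matters little, because the ratings are analysed separately and no combined score is planned.

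**Deliberate choice.** Section 6.2 says that measurement methods follow the earlier pivotal studies, so the relief wording may be inherited. That is a reason to offer a second remedy. It does not make the answers fit the question.

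**Conclusion.** The point holds as a mismatch between question and answers on one component of a secondary endpoint. Worsened and unchanged subjects share one score, so the item cannot show a between-arm difference in worsening in either direction. This follows from the wording alone and needs no assumed rates.

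It is a minor correction. Both blinded arms use the same scale, so the rank test remains valid and type I error is not inflated. The primary Day 3 helpfulness rating and the sample size do not depend on the item. No power figure should be attached to it, because the sign and size of any effect rest on worsening rates that the protocol does not give.

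A reader might also infer that the answers were copied by mistake from the local-pain item. The wording is identical, but the text does not show whether this was an error or a carry-over from earlier studies.

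**What to change.** Before the diary is used, give the restriction-of-movement item in 9.1.6 and in the diary the answers already used for activities of daily living: 1 = worsening, 2 = no change, 3 = mild, 4 = moderate, 5 = marked improvement.

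If the relief scale must be kept for comparability with the earlier pivotal studies, reword the question to ask for relief in restriction of movement, and state that worsening is scored as *no relief*. The item would still not show worsening, but its meaning would be clear.

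Either way the cost is a wording change in two places. The first option loses the *complete relief* level, leaving three grades of benefit instead of four, and may lose item-level comparability with the earlier studies. Once diaries have been completed on the present scale, the distinction cannot be recovered from this item.
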